Appendix A: Eligibility Checklist

MRN: _____

Enrollment Date: ____/____/201____ Enrollment Time: ____:

Inclusions: All must be “yes” or do not enroll participant	Yes	No
Patient self-reports a history of difficult IV access		
Patient has a history of AT LEAST ONE of the following: (indicate which patient meets)		
Pt. recounts a prior emergency room visit/hospitalization when > 2 sticks required to obtain access		
History of a rescue catheter (such as US-guided IV, PICC line, midline, or CVC) ESRD on dialysis		
History of IV Drug		
Use History of Sickle Cell		
Patient is 18 years of age or older		

Exclusions: All must be “no” or do not enroll participant	Yes	No
Patient is under the age of 18 years of age		
Patient refuses to participate in the study		
Previous Inclusion in the study		
Cognitively impaired		

Form Completed by: _____ (Printed name) _____ (Signature)

Date: _____ Time: _____

Principal Investigator: _____ (Printed name) _____ (Signature)

Date: _____ Time: _____

Appendix B: Insertion-Related Data

Research Staff completing form (signature/date): _____

Catheter Type (circle): Ultra Long IV Standard IV

	Depth (cm)	Diameter (cm)	# Attempts	Depth (cm)	Diameter (cm)	# Attempts
	1 st Venous Access point				2nd Venous Access point	
Inserter #1 ID:						
	1 st Venous Access point				2nd Venous Access point	
Inserter #2 ID:						

[figure not shown]
Minutes for procedure completion (time from needle to skin to dressing site): _____

Time at Completion of Insertion: _____

Initial EC Vitals: BP _____ HR _____

Gender: _____ Age: _____ BMI: _____

Location of Successful Cannulation
(Mark 1/2/3 for access attempts, circle successful site): Left Right

Insertion site distance from AC fossa (cm): _____

Disposition (Circle): Observation Regular Progressive ICU Discharge

Appendix C: Functionality and Complications

Day	Functional 1: draw 2: flush 3: infusing 4: failed	Removal Time	Reason for Remov al	Venous Doppler 1: + for dvt 2: + for svt 3: + for dvt/svt 4: - for both 5: none	Lab confirmed infection Y/N	Discharge <24 hrs from insertion	Replacement Access in the case of failure 1: Midline 2: PICC 3: PIV 4: US PIV 5: CVC	Research staff initials
1								
2								
3								
4								
5								
6								
7								
8								
9								
10								
11								
12								
13								
14								
15								
16								
17								
18								
19								
20								
21								
22								
23								
24								
25								
26								
27								
28								
29								
30								

Reasons for Removal: (1) Completion of therapy; (2) infiltration; (3) infection; (4) dislodgement; (5) leaking; (6) pain; (7) other; (8) unknown

Post processing data

Angle of Insertion (°)	Length in vein (cm)	% Length in Vein

Signature/Date: _____

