A variable that may alter the survival of US-guided IVs that has not been studied extensively is the length of catheter that resides in the vein. Currently the general accepted rule is that an "adequate" amount of the catheter should be in the vein to avoid failure of the catheter.¹¹⁻¹⁴ However, this recommendation is only anecdotal and there has been no study to verify or quantify it. Our preliminary data focused on defining this relationship. In our study, **100% of catheters failed** in which less than 30% of the catheter was placed within the vein and **no failures** in those IVs in which at least 65% of the catheter was in the vein. All catheters in this analysis were commonly available 4.78 cm IVs. A key challenge for inserters is that achieving this quantity of catheter length in vein is impractical at the recommended angle of insertion when considering deeper target vessels. For many institutions, including ours, the 4.78 option is the longest stocked IV catheter and catheter survival is negatively impacted.

Central Hypothesis/Objectives:

We hypothesize that using an Ultra Long IV (6.35 cm) catheter increases the likelihood of ensuring a higher quantity of the catheter in the vessel lumen and leads to improved catheter longevity.

Primary Objective: Compare the IV survival between the Ultra Long IV (UL IV) (6.35 cm/20G) and the Standard Long IV (SL IV) (4.78 cm/20G) placed under US-guidance.

Function is defined as ability of catheter to flush 5 mL without resistance with or without blood sampling.

Secondary/Tertiary Objective(s):

Determine catheter survival based on vein depth.

Determine optimal cutoff length of catheter in vein for best survival profile.

Determine catheter survival based on angle of insertion.

Quantify specific etiologies related to premature catheter failure comparing UL IV to the SL IV.

Quantify overall costs associated with placement of the UL IV compared to the SL IV.

Determine overall success of placement UL IV versus SL IV.

Determine first-stick success UL IV compared to SLIV.

Determine number of attempts and time to insertion comparing UL IV to SL IV.

Safety Endpoint(s):

Compare phlebitis and thrombosis complication rates between the Ultra Long IV and the Standard Long IV.

[figure not shown]
Compare infection rates for all catheters.

Study Design:

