Staff members are expected to attempt a minimum of 3 attempts before enlisting another provider for help. A functional IV is confirmed by extraction of 5 mL of nonpulsatile blood and low-resistance infusion of a 5 mL normal saline flush without evidence of extravasation. Other data variables collected include: inserter details, need for rescue inserter, patient pertinent medical history, vitals, age, sex, first-stick success, cannulation success or failure, vein diameter, catheter in vein longitudinal measurement, angle of insertion, number of venous access attempts, time of IV insertion, time to IV insertion, location of IV insertion, distance of IV insertion from the antecubital fossa, medications infused, ionic contrast injection for computed tomography. A venous access attempt is defined as each time the needle punctures the skin. Once the IV is secured, research staff will measure distance from the puncture or catheter insertion site to the antecubital fossa to quantify the site to antecubital measurement. See Appendix B for Data Collection Tool for insertion-related variables.

Follow-up Assessment

After initial assessment, the catheter will be assessed by the research team every 24 hours as long as the patient is hospitalized. At each follow up interval the researcher notes the date/time of evaluation and assesses for any signs and symptoms of complications and functionality of the device. A catheter is functional if the IV flushes without resistance. Catheters will be assessed daily for signs and symptoms of complications. See Appendix C for details regarding the assessment for functionality and complications. Any signs or symptoms of complications or lack of functionality will be reported to the patient's primary care team so that management of the IV catheter can be addressed.

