If the catheter was identified to have any signs or symptoms of complications during follow-up assessment the date and time of observation of the complication will be documented in the data collection tool and the primary team will be notified of the complication. If the catheter was removed prior to the follow-up assessment then the IV removal time and the reason for removal will be obtained through chart review. For all catheters removed due to a complication, re-insertion attempt data will be tracked through the medical record in the nursing section for venous lines and need for reinsertion of the IV or escalation to a midline, PICC, or CVC will be noted. If the patient is discharged prior to the time of follow-up assessment then the time of discharge will be documented and the IV will be presumed functional until time of discharge unless otherwise noted in the chart.

The medication administration record will be queried for all medications given through each catheter. Vesicants/irritants that are generally given via central line or considered caustic to the vessel will be noted in both groups. Number of doses will be recorded. See Appendix D for full list of non-neoplastic vesicants/irritants.

Additional data gathered by research staff on follow-up evaluation includes: dwell time in days/hours, hospital length of stay, and number of peripheral IVs or rescue catheters for duration of stay.

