Appendix E represents the data collection documentation tool for all medications.

SVT and DVT rates will be calculated based on upper extremity proven diagnosis of SVT and/or DVT in symptomatic cases. Researchers will review all study subject records in EPIC and screen for all upper extremity venous Doppler examinations. Radiology interpretations will be reviewed for findings of consistent with thrombus. This review will occur thirty days post patient discharge.

Infection rate will be tracked using confirmed blood stream infection data from epidemiology. These are cases in which line sepsis or bacteremia is confirmed by positive blood cultures.

Cost difference between approaches will be tracked. Equipment costs and personnel costs will be tracked. Number and type of IV catheters inserted/attempted will be extracted from the medical record. Supply costs will be estimated based on number of IVs attempted. Median time to successful catheter placement will serve as a baseline for estimating time needed for future reinsertions. Time will be assigned a monetary value. We will also track the number of patients from each group that require a PICC or CVC as a rescue catheter.

Sample Size and Power Analysis:

For this randomly allocated two-groups experiment, the primary outcome is catheter survival. Sample size calculation is based on primary outcome: composite or all cause premature removal due to complication of the IV catheter. Based on literatures and a new published article immediately prior to study period, we estimate sample size using the median survival time 30 hours for the 4.78 cm standard IV option. 91 subjects per group for a total sample size of 182 subjects is the minimum recommendation assuming a 10% dropout rate. This calculation

achieves power of 80% to detect a hazard ratio of 0.63 or less for line failure of the 6.35 cm ultra long IV based on log-rank test.

Statistical Analysis:

Characteristics of enrolled and eligible patients will be summarized between two arms using means [standard deviations] and medians [interquartile ranges] compared by t-tests or Wilcoxon tests for continuous variables and frequencies (percentages) compared by chi-squared tests or Fisher's exact tests for categorical variables.

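### The removal-reason list has no code for a catheter that will not flush, nor for phlebitis, so these causes cannot be separated reliably by arm for the exploratory etiology objective

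*Combined protocol and SAP*

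**What the plan says.** Under the Primary Objective: "Function is defined as ability of catheter to flush 5 mL without resistance with or without blood sampling". Follow-up Assessment repeats the test: "A catheter is functional if the IV flushes without resistance". Among the Secondary/Tertiary Objectives is: "Quantify specific etiologies related to premature catheter failure comparing UL IV to the SL IV". Under Safety Endpoint(s), phlebitis and thrombosis rates are to be compared between the arms.

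For the method of recording, Follow-up Assessment says: "See Appendix C for details regarding the assessment for functionality and complications". Appendix C contains only the form and its codes. The daily status column reads "Functional 1: draw 2: flush 3: infusing 4: failed", and the cause list reads "Reasons for Removal: (1) Completion of therapy; (2) infiltration; (3) infection; (4) dislodgement; (5) leaking; (6) pain; (7) other; (8) unknown". The same form has columns for removal time, venous Doppler result, laboratory-confirmed infection, discharge within 24 hours, and the type of replacement access after a failure.

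The catheter is assessed every 24 hours. If it was removed before the visit, "the IV removal time and the reason for removal will be obtained through chart review". Sample Size and Power Analysis words the primary outcome as "composite or all cause premature removal due to complication of the IV catheter".

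**The concern.** Flushing is the one functional test applied at every follow-up visit, yet the cause list has no entry for failing it. A catheter that will not flush, with no infiltration, leak, dislodgement, infection or pain, has only codes 7 (other) and 8 (unknown) available. Those codes also receive every unlisted complication and any removal for a reason that is neither a complication nor completion of therapy.

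The trial's hypothesis is mechanical: more catheter in the vein should mean longer survival. The etiology objective is where the trial would see which failure modes change, and whether a gain in one is offset by a loss in another. If blockage is merged with unrelated reasons, that comparison is blurred for blockage. Phlebitis has the same problem: it is named for comparison between arms, but the form has neither a removal code nor a column for it.

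**Working it through.** No figure in the plan bears on this point, so the check sets the definitions, the objective and the form side by side. The table shows what the Appendix C form would hold in each case.

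| Case | Functional column | Removal reason | Cause readable from the form? |
|---|---|---|---|
| Infiltrated, found at visit | 4 | 2 | Yes |
| Will not flush, nothing else found, seen at visit | 4 | 7 or 8 | No |
| Another unlisted complication ends function, seen at visit | 4 | 7 | No; can look the same as the row above |
| Will not flush, removed between visits | possibly no failed result | 7 or 8, from chart | No |
| Phlebitis | any | 6, 7 or 8 | No |
| Unlisted non-complication removal | 1 to 3 | 7 | Not as a failure, but no code says so |

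Three steps follow.

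1. *Status is not cause.* Code 4 can apply to infiltrated, leaking or blocked catheters alike. The replacement-access column says what was placed next. Neither identifies the reason.

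2. *Combining columns gives only a bound.* For failures seen at a visit, let O be the number in an arm with status 4 and reason 7 or 8. Then O = F + X, where F is no-flush failures without another identified cause and X is all other unlisted or unknown causes. O is at most an upper bound for F. Between arms, O(UL) − O(SL) = [F(UL) − F(SL)] + [X(UL) − X(SL)]. The form does not identify the last term, so the difference in O does not bound the difference in F.

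3. *Some failures may have no flush result.* Between-visit removals rely on the chart. As an indication only, take the plan's 30-hour median for the standard catheter and assume exponential failure times. The proportion failing within 24 hours is 1 − 2^(−24/30) = 1 − 0.574 = 0.426, about 43%. This is not the proportion removed before a visit, which the documents do not give. It shows only that early failures need not be rare under the plan's own assumption.

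The Statistical Analysis section promises proportions by arm for SVT, DVT and infection. It does not mention phlebitis or a table of removal causes, so nothing there supplies the missing classification.

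**The case against.** The strongest reply is that the form separates status from cause on purpose, which is a defensible design. Failure to flush is often a sign of something else, such as infiltration, dislodgement or thrombus, and those have their own codes or columns. Follow-up Assessment also calls for the date and time of any observed complication to be documented, and chart review may supply a reason. A removal coded other can be partly sorted: with status 4 or a replacement entry it looks like a failure, and with neither it does not. The protocol's Study Design calls the secondary and tertiary objectives exploratory.

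Most of this stands, and it limits the point. A reader might infer that the etiology objective cannot be met at all, or that the comparison is not estimable. The documents do not support that: the status, Doppler, infection and replacement columns and the chart carry relevant information. A reader might also take failure to flush as the trial's definition of failure. The protocol defines function that way, but words the primary outcome more broadly, as removal due to complication. Nor does the missing code invalidate the log-rank comparison, which needs the time of failure and whether it occurred, not this code.

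What the reply does not remove is the residual group: catheters that stop flushing with no other cause found. For these the available columns give an approximate count or an upper bound, and between-visit removals may lack even that.

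**Conclusion.** The point holds in a limited form. Appendix C lacks codes for occlusion or inability to flush and for phlebitis. Flush failures without another identified cause fall into other or unknown; phlebitis may also be absorbed into pain. Neither can be separated reliably by arm from the form.

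The effect is confined to the exploratory etiology comparison and to how phlebitis is recorded as a safety endpoint. A removal coded as other does not by itself show whether it was due to a complication, so some event classification rests on the other columns and on judgement; that is a reason to tidy the codes, not evidence that the primary analysis fails.

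The size cannot be stated as a number of events, because the documents give no share of failures due to flush failure. The conclusion rests on the form as printed, with no specify field for other and no further instruction on how a failed status maps to a cause. It does not depend on the exponential illustration. The change is worth making because a stated objective depends on it and it costs little.

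**What to change.** In Appendix C:

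- Add a removal/failure code for a catheter that does not flush or flushes with resistance, with no other cause identified.
- Add a code for phlebitis.
- Split other into other complication and non-complication removal, each with a specify field.
- Require a cause whenever the Functional column is scored 4, as well as at removal.

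In Statistical Analysis, state that cause-specific counts will be tabulated by arm using these codes.

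The cost is a minor form revision, with no added visits or procedures. Records already collected can be recoded only in part, from the daily status and the chart, as far as chart detail allows. The report should say how many removals stay in the residual codes in each arm.

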Appendix D: List of Vesicants (Red) and Irritants (Yellow)

RED LIST	YELLOW LIST
Well-recognized vesicants with multiple citations and reports of tissue damage upon extravasation	Vesicants associated with fewer published reports of extravasation; published drug information and infusate characteristics indicate caution and potential for tissue damage
Calcium chloride	Acyclovir
Calcium gluconate	Amiodarone
Contrast media - nonionic	Arginine
Dextrose concentration $\geq 12.5\%$	Dextrose concentration $\geq 10\% \text{ to } 12.5\%$
Dobutamine	Mannitol $\geq 20\%$
Dopamine	Nafcillin
Epinephrine	Pentamidine
Norepinephrine	Pentobarbital sodium
Parenteral nutrition solutions exceeding 900 mOsm/L	Phenobarbital sodium
Phenylephrine	Potassium $\geq 60 \text{ mEq/L}$
Phenytoin	Vancomycin hydrochloride
Promethazine	
Sodium bicarbonate	
Sodium chloride $\geq 3\%$	
Vasopressin	

Appendix E: Medications

Day	Medications transfused via catheter
1	
2	
3	
4	
5	
6	
7	
8	
9	
10	
11	
12	
13	
14	
15	
16	
17	
18	
19	
20	
21	
22	
23	
24	
25	
26	
27	
28	
29	
30
